Study Protocol and Statistical Analysis

[figure not shown]
A. Study Protocol

1. Research subjects

The research subjects were patients with CHB receiving ETV or second-line NA (LAM/ADV/LdT) who were admitted to The Second Affiliated Hospital of Chongqing Medical University and other centers.

2. Research design

96-week multi-centre prospective real world study

3. Research methods

In our hospital, about 150 patients are screened for HBV-DNA every day. Therefore, 54 million patients will be tested for HBV-DNA within one year, of which 30% are estimated to be HBV-DNA ≥ 10 IU. These patients will be informed to the Department of Infectious Diseases of the Second Affiliated Hospital of Chongqing Medical University for follow-up, and will be randomly divided into three groups according to 1:1. Patients in all three groups will be educated about hepatitis B virus infection and antiviral treatment, and the treatment regimen will be adjusted according to whether their HBV DNA is ≥ 10 IU/ml or not. Patients in group 1: patients with persistent low level HBV DNA (< 10 IU/ml). Patients in group 2: HBV-DNA ≥ 10 IU/ml, receiving HBV-related education and being advised by the doctor to change or to add another NA. Patients in group 2: patients with persistent HBV DNA (> 10 IU/ml) but refuse to change the regimen. Patients in group 3: patients with persistent HBV DNA (> 10 IU/ml) and agree to change the regimen. Educational methods include videos, including an introduction to hepatitis B virus (disease profile, infection, outcome, HBV infection, vertical transmission and other risk factors) for 5 minutes, brochures with relevant information and consultations with physicians and nurses.

All patients with CHB receiving ETV or second-line NA (LAM/ADV/LdT) treatment for more than six months to one year will receive HBV-DNA

detection, and patients with HBV-DNA \geq 10 IU/ml will be informed and recommended to adjust the treatment regimen so that we could obtain the actual prevalence of HBV-DNA load $<$ 10 IU/ml in Chongqing HBV cohort. We estimated that 30% of the patients had HBV-DNA \geq 10 IU/ml, so there were about 16,200 patients had HBV-DNA \geq 10 IU/ml among 54,000 patients a year. These patients will be diagnosed with LLV and will undergo a treatment regimen adjustment, with a recommendation to switch to or use a different type of NA for viral treatment.

4. Outcome indexes

(i) The main index:

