The proportion of patients who received a complete virologic response (HBV DNA $<$ 10 IU/ml) at 24 weeks after therapy adjustment.

(ii) The secondary index:

1. The proportion of patients with complete virologic response (HBV DNA $<$ 10 IU/ml) at 12 weeks, 48 weeks and 96 weeks after therapy adjustment.

2. The proportion of patients with normal ALT at baseline and at each follow-up time point.

3. Changes of bone and kidney indicators (eGFR, SCr, BMD, etc.) compared with baseline at each follow-up time point.

B. Statistical Analysis

1. Statistical description

. Whether the measurement data conforms to normal distribution: the statistical method is modified or the data is converted when the measurement data does not conform to normal distribution, then it is managed as normal distribution when the mean and median are close due to the large sample size because of the opening test. Outliers: Statistical and professional analysis is performed to determine whether to keep outliers. Management of missing value in major efficacy indicators data: when a major efficacy data is missing in individual subjects, the method of filling is determined from a statistical and professional perspective. If the case is lost, data from the previous measurement shall be transferred.

. Case analysis of unfinished tests: the reason of lost cases should be analyzed one by one.

. Descriptive statistics: indicating the mean, the standard deviation, the maximum, the minimum, the median, the upper and lower quartile (Q1 and Q3), the confidence interval, the frequency (composition ratio), etc.

2. Statistical inference method

. The measurement data: T test, paired T test, rank sum test, paired

rank sum test, correlation analysis was used. The counting data: Chi-square test, Fisher exact test, etc. The grade data were tested by CMH method.

3. Statistical expression

- . The report is mainly expressed in tables, which are self-explanatory, that is, with headings, notes and main statistical indicators.
- . The results of repeated measurements are presented in tables with statistical charts for readability. F value and P value of an OVA of repeated measurement data are added.
- . Bilateral tests are generally used for statistical tests, and P less than or equal to 0.05 is considered to be statistically significant.

4. Statistical software

SPSS22.0 software will be used for analysis.

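### The virologic indexes are timed from a therapy adjustment that refusers and group 1 do not have, no contrast is named, and the stated random allocation does not match how the groups are formed.

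*Combined protocol and SAP*

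**What the plan says.** Section A.4 defines the main index as the proportion with HBV DNA below 10 IU/ml "at 24 weeks after therapy adjustment". The secondary virologic index is the same proportion "at 12 weeks, 48 weeks and 96 weeks after therapy adjustment". Neither names a group, a reference group or an effect measure. The other secondary indexes use a different anchor: "The proportion of patients with normal ALT at baseline and at each follow-up time point", and bone and kidney changes "compared with baseline at each follow-up time point". Baseline is not defined.

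Section A.3 describes three groups.
- Group 1: "Patients in group 1: patients with persistent low level HBV DNA (< 10 IU/ml").
- Group 2 is described twice. One sentence has patients at or above 10 IU/ml "receiving HBV-related education and being advised by the doctor to change or to add another NA". The next reads "Patients in group 2: patients with persistent HBV DNA (> 10 IU/ml) but refuse to change the regimen".
- Group 3: patients with persistent HBV DNA above 10 IU/ml who agree to the change.

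The same section says patients are divided at random, 1:1, into the three groups, and that "the treatment regimen will be adjusted according to whether their HBV DNA is ≥ 10 IU/ml or not". It says in one place that patients at or above 10 IU/ml are recommended an adjustment, and in another that they will undergo one. For count data, section B.2 lists the chi-square and Fisher exact tests, with no groups named and no adjustment for covariates.

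**The concern.** A week-24 proportion needs a day 0 for everyone in its denominator. Refusers never have an adjustment, so their week 24 has no defined start. Group 1 falls outside the rule that triggers an adjustment. It is also selected on the response criterion itself, so in that group the index can only measure maintained suppression.

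Three groups, one of them made up of refusers, suggest that a comparison is intended. If so, two things are open. First, the analyst could choose after seeing the data between a group 3 proportion, a three-group test and group 3 versus group 2, and could date the refusers' week 24 from any visit. Second, the patient's decision separates groups 2 and 3, so differences in baseline viraemia, current drug or treatment history go straight into an unadjusted test. The statement of random allocation would lead a reader to take such a difference as causal.

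**Working it through.** **1. Which groups have the date.**

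| Group | Formed by | Adjustment date | Meets response criterion at entry |
|---|---|---|---|
| 1 | viral load | none described | yes |
| 2 (refusers) | viral load, then patient decision | none, by definition | no |
| 3 (acceptors) | viral load, then patient decision | yes | no |

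The first group 2 sentence, on advice, also covers acceptors and so does not supply a date for refusers. The sentence saying that patients at or above 10 IU/ml will undergo adjustment would give everyone above the threshold a date, but it conflicts with the refuser definition. Viral load and patient decision fill every row, which leaves nothing for random allocation to decide.

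**2. The plan's only count.** 150 per day × 360 days = 54,000, and 0.30 × 54,000 = 16,200 patients a year at or above 10 IU/ml. This matches section A.3 (the figure of 54 million elsewhere in that section does not). It is a screening count. The plan gives no sample size, response rate or delay, so every input in steps 3 and 4 is an assumption, and both steps assume that changing regimen has no effect.

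**3. Clock offset.** Assume refusers are clocked from the offer and acceptors from a change *d* weeks later, acceptors stay in group 3 whatever happens before the change, and suppression arises at a constant rate giving 30% at 24 weeks.
- Permanent suppression: h = −ln(0.70)/24 = 0.01486 per week; group 3 = 1 − exp(−h(24 + d)); group 2 = 0.30.
  - d = 4: 0.3404, +4 points.
  - d = 12: 0.4143, +11 points.
- With weekly rebound rate r: P(t) = h/(h + r) × [1 − exp(−(h + r)t)], with h re-solved so that P(24) = 0.30.

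| r per week | d = 4 | d = 12 |
|---|---|---|
| 0.01 | 0.3337 (+3) | 0.3911 (+9) |
| 0.03 | 0.3227 (+2) | 0.3562 (+6) |
| 0.05 | 0.3147 (+1) | 0.3335 (+3) |

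With one time zero, d = 0 and the difference is 0.

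**4. Self-selection.** Assume lower-viraemia patients respond in 60% and others in 20%, and that 40% of acceptors but 60% of refusers have lower viraemia.
- Group 3: 0.4 × 0.6 + 0.6 × 0.2 = 0.36.
- Group 2: 0.6 × 0.6 + 0.4 × 0.2 = 0.44.
- Reversing the imbalance reverses the sign.

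If 1% or 10% of the 16,200 enrol in two equal groups, each group has 162/2 = 81 or 1,620/2 = 810. Exact enumeration of the Pearson chi-square test at two-sided 0.05 gives these rejection rates:

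| Assumed proportions | 81 per group | 810 per group |
|---|---|---|
| 0.36 vs 0.44 | 0.175 | 0.909 |
| 0.38 vs 0.42 (45%/55% imbalance) | 0.078 | 0.378 |
| 0.44 vs 0.46 (40%/60% imbalance; response 50%/40%) | 0.056 | 0.125 |

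**The case against.** The strongest answer is that no comparison is intended. Section A.2 calls this a real-world study, and section B.1 lists frequencies and confidence intervals as descriptive output. Read literally, the main index is a proportion in group 3, the one group with an adjustment date. On that reading refusers and group 1 need no time zero for the main index. This stands as a qualification: the clock and contrast problem depends on a comparison being meant. It does not dispose of the point, because the plan never restricts the index to group 3, and the random-allocation statement conflicts with the group definitions on either reading.

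A reader might go further and infer that the main index cannot be evaluated at all, or that the result will be biased in favour of changing regimen. The documents support neither. The group 3 proportion can be evaluated, and nothing in the documents fixes the size or direction of any bias.

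It is also fair to say that the arithmetic only illustrates. The clock figures shrink once rebound is allowed, and the self-selection figures depend on an assumed imbalance. Finally, the mismatch of at-or-above 10 with above 10 is minor, the doubled group 2 sentence may be a drafting slip, and one figure ahead of section A is not shown, so its content could not be checked.

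**Conclusion.** The point holds in two parts. Unconditionally, the statement of random allocation contradicts groups defined by viral load and patient decision, and the virologic indexes are timed from an event that only group 3 clearly has. Conditionally on a comparison, which the three-group design suggests but the plan does not state, the listed unadjusted tests would set self-selected groups against each other on clocks that may differ.

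Under the stated assumptions and no switch effect, the clock alone gives +4 or +11 points for a 4- or 12-week offset with permanent suppression. With 1% to 5% weekly rebound this falls to about +3 to +1 or +9 to +3. Self-selection giving 36% versus 44% is declared significant in 17% of tests at 81 per group and 91% at 810; milder imbalances give less. These numbers show that the effect can matter; they do not estimate it. If only group 3 is described, there is no false comparison, but also no evidence on whether changing regimen improves response.

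**What to change.** 1. Replace the random-allocation statement in section A.3 with one saying that groups are formed by viral load and patient decision. Reconcile the two group 2 sentences, the text that patients will undergo adjustment with the text that they are recommended it and may refuse, and at-or-above 10 with above 10 IU/ml.
2. Name group 3 versus group 2 as the primary contrast for HBV DNA below 10 IU/ml at week 24. Set time zero in both groups at the visit where adjustment is offered and accepted or declined. Fix membership at that decision and analyse patients in that group whatever happens later. Use the same anchor for weeks 12, 48 and 96, and as baseline for ALT, kidney and bone.
3. Report an adjusted risk difference with a 95% CI, standardised from a logistic model with baseline HBV DNA, current NA, prior treatment duration, baseline ALT and centre, as far as these are recorded. Label it a non-randomised comparison with possible residual confounding.
4. Leave group 1 out of the response test and describe its maintained suppression.

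If only a group 3 description is meant, say so, give the proportion with a 95% CI and make no comparative claim.

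**Cost.** Decisions must be dated and covariates recorded. Refusers need HBV DNA at the same weeks, which may mean added visits; the legible text shows no visit schedule, and one figure is not shown. Some group 3 patients will have had less than 24 weeks on the new regimen at week 24. Later switchers and never-switchers dilute the contrast, and adjustment cannot remove unmeasured differences between acceptors and refusers.

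### The normal-ALT index makes no use of baseline ALT status, so an unadjusted comparison of self-selected groups 2 and 3 could reflect who was normal at the start

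*Combined protocol and SAP*

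**What the plan says.** Section A.4 lists as secondary index 2 "The proportion of patients with normal ALT at baseline and at each follow-up time point". The denominator is not limited to patients with abnormal ALT at entry, and patients who move from abnormal to normal are not separated from those who were normal throughout. The index names no contrast: it does not say whether ALT is to be compared between groups, compared with baseline, or only described.

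For binary outcomes section B.2 gives "The counting data: Chi-square test, Fisher exact test, etc". Paired tests appear only for continuous data: "The measurement data: T test, paired T test, rank sum test, paired" rank sum test. CMH is assigned to graded data. Section B.3 says "The results of repeated measurements are presented in tables with statistical charts for readability" and adds ANOVA F and P values, but gives no repeated-measures method for a binary outcome. No regression, covariate adjustment or stratification by baseline ALT is named. The test level is in B.3: "Bilateral tests are generally used for statistical tests, and P less than or equal to 0.05 is considered to be statistically significant".

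Section A.3 says patients "will be randomly divided into three groups according to 1:1". It then describes one group as "patients with persistent HBV DNA (> 10 IU/ml) but refuse to change the regimen" (group 2) and another as "patients with persistent HBV DNA (> 10 IU/ml) and agree to change the regimen" (group 3). The label for group 2 is used twice there, with different descriptions; I take the refuse/agree pair as the working definitions.

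**The concern.** Patients who refuse a change of regimen and patients who accept one may well differ in ALT at entry, and nothing in the refuse/agree definitions makes them alike. Most patients with normal ALT at entry can be expected to have normal ALT later, so a group that starts with more of them will tend to show a higher proportion at follow-up whatever the treatment does. Printing the baseline proportion beside the follow-up proportion lets a reader see the imbalance, but does not take it out of a chi-square test at the later visit. At stake is a secondary conclusion about ALT that could be spurious, or could hide a true benefit.

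There is also a question of meaning. One all-patient proportion mixes two events: abnormal ALT becoming normal, and normal ALT being kept. A single number cannot show which of them moved.

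**Working it through.** **The only size figure in the documents.** Section A.3: 150 patients a day × 360 days = 54,000 a year, and 54,000 × 0.30 = 16,200 with HBV DNA at or above 10 IU/ml. Both reproduce. (The 54 million in the same section is a thousand-fold slip and plays no part here.) This is a throughput estimate; no sample size per group is stated.

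**Assumed inputs.** The documents give no ALT rates, so every rate below is an assumption. Let q be the share normal at baseline, s the chance that a normal patient stays normal, and r the chance that an abnormal patient normalises. The follow-up proportion is q·s + (1 − q)·r.

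**Baseline imbalance, no treatment effect.** Take s = 0.95 and r = 0.50 in both groups, with q = 0.75 in group 3 and 0.85 in group 2.
- Group 3: 0.75 × 0.95 + 0.25 × 0.50 = 0.8375
- Group 2: 0.85 × 0.95 + 0.15 × 0.50 = 0.8825
- Crude difference: −0.045, that is −4.5 points

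In general the spurious difference is (q₃ − q₂)(s − r). With r = 0.30 and 70% normal in one group against 65%, 60% or 50% in the other, it is 3.3, 6.5 or 13 points. The size depends on these inputs, but it is zero only if q is equal in the two groups or s equals r.

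A larger sample does not help. For the −4.5-point case, a two-sided 0.05 test of two proportions rejects about 35% of the time at 300 per group, 83% at 1,000 and 98% at 2,000 (illustrative sizes).

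**Baseline imbalance with a true benefit.** Keep q and s, and let r be 0.60 in group 3 and 0.40 in group 2.
- Group 3: 0.75 × 0.95 + 0.25 × 0.60 = 0.8625
- Group 2: 0.85 × 0.95 + 0.15 × 0.40 = 0.8675
- Crude difference: −0.5 points, despite a 20-point benefit among abnormal patients

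**Blending of two events.** With equal q in both groups, the crude difference is q(s₃ − s₂) + (1 − q)(r₃ − r₂). If retention is equal, the first term vanishes and the difference is the effect among abnormal patients times the abnormal share: 0.20 × 0.20 = 4 points at q = 0.80, and 0.30 × 0.20 = 6 points at q = 0.70. If retention is 95% v 90% and q = 0.80, it is 0.80 × 0.05 + 0.20 × 0.20 = 8 points, of which half comes from patients who were normal at entry.

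**Pairing, only if a baseline-to-visit test is done.** Under no change and within-patient correlation ρ, the true variance of the difference is (1 − ρ) times the one an unpaired test uses. The true type I error is therefore 2[1 − Φ(1.96/√(1 − ρ))]: about 1.9% at ρ = 0.3, 0.6% at ρ = 0.5 and 0.03% at ρ = 0.7, against a nominal 5%. The unpaired test is conservative.

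**The case against.** The strongest reply is that the plan commits to no faulty analysis. Index 2 states no contrast, whereas index 3 beside it speaks of comparison with baseline. The list of tests for counts is open-ended, so McNemar or a model is not excluded. That stands: the gap is in what the plan specifies, and the plan does not prescribe a wrong test. The baseline proportion is also part of the index, so baseline ALT is not wholly ignored. It remains true that the only tests named for counts are unadjusted and unpaired.

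A reader might infer that the ALT result will have wrong error bars. The documents do not support that. A between-group chi-square at one visit, or an interval for one proportion at one visit, has a valid standard error. The pairing fault arises only in a within-group baseline-to-visit test, which index 2 does not specify, and there it makes the test too cautious.

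A reader might also infer that the index is bound to be diluted and underpowered. That needs equal retention and a sample size, and the documents give neither. With 88% v 84% normal at follow-up, power is 29% at an assumed 300 per group but about 91% at 1,620 per group. Patients normal at baseline cannot improve, but they can worsen, and the all-patient proportion captures that. Which of these to treat as the main efficacy reading is a choice of estimand, not an error.

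Finally, no data in the documents show that baseline ALT will differ between groups, and the contradiction between random division and refuse/agree groups is a wider defect that affects every outcome. Both points are fair. The exposure to imbalance follows from how the groups are defined; its size is unknown.

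**Conclusion.** The point holds as a vulnerability to baseline imbalance combined with under-specification. If groups 2 and 3 are formed by patient choice, an unadjusted comparison of normal ALT at follow-up carries any baseline difference with it. Under the assumed 75% v 85% normal at entry, 95% retention and 50% normalisation, that is −4.5 points with no true effect. With the same imbalance and retention, a true 20-point benefit among abnormal patients shows as −0.5 points. These figures illustrate the mechanism and do not predict this trial's result. If the groups were in fact randomised, only chance imbalance would remain, which is why the two statements in section A.3 must be reconciled. The blending of normalisation with retention is a problem of interpretation whichever way the groups are formed. The outcome is secondary, but baseline ALT is already part of the index, so the change is worth making.

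**What to change.** 1. Keep the descriptive proportions at baseline and each visit.
2. State the between-group contrast: group 3 v group 2, by logistic regression at a named visit, or GEE across visits, adjusted for baseline ALT status.
3. Tabulate separately, by group and visit, normalisation among patients abnormal at baseline and loss of normal ALT among patients normal at baseline. Reporting both avoids discarding deterioration.
4. If any within-group baseline-to-visit test is done, name McNemar's test.
5. Reconcile the random 1:1 sentence in section A.3 with the groups defined by refusing or agreeing.

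The cost is a little more analysis on data already planned for collection, and smaller numbers in the two subset tables. Adjusting for baseline ALT alone does not remove other confounding from self-selection, so the adjusted comparison should still be reported as non-randomised if the groups are formed by choice.

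### Lost patients' previous HBV DNA value is carried forward into the week-24 response with no sensitivity analysis, which biases the proportion whenever their status would have changed

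*Combined protocol and SAP*

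**What the plan says.** Section B.1 (Statistical description) has a provision headed "Management of missing value in major efficacy indicators data". It contains two rules. For a missing value in an individual subject, "the method of filling is determined from a statistical and professional perspective". For a lost patient, "If the case is lost, data from the previous measurement shall be transferred". The first fixes no method in advance; the second is last observation carried forward. The only other provision is that "the reason of lost cases should be analyzed one by one". Part B names no sensitivity analysis, missing-data assumption or expected rate of loss.

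Under A.4 the main index is the proportion with HBV DNA below 10 IU/ml "at 24 weeks after therapy adjustment", so the rules apply to it. The secondary index repeats the proportion "at 12 weeks, 48 weeks and 96 weeks after therapy adjustment", which makes week 12 the only outcome time point between baseline and week 24. No other visit schedule is given.

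A.3 places group 1 below 10 IU/ml and groups 2 and 3 at or above it. It says that patients "will be randomly divided into three groups according to 1:1", yet it also defines groups 2 and 3 by refusal of, or agreement to, a change of regimen. Group 2 has a second definition as well: patients "receiving HBV-related education and being advised by the doctor to change or to add another NA". No primary comparison is named.

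**The concern.** Carrying a value forward assumes that a lost patient's response status stays as it was when last seen. The plan neither states nor tests this. It fits poorly with an endpoint in which groups 2 and 3 begin as non-responders by definition: if baseline counts as the previous measurement, a patient lost before week 12 is scored a failure, and one lost between weeks 12 and 24 keeps the week-12 result. If response is still rising, both understate the week-24 rate. In group 1 the baseline value has the opposite effect, because it always scores a response.

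At stake is the main index itself and, if groups 2 and 3 are compared, part of any modest difference between them. Reviewing reasons for loss is useful but changes no scored value. The open-ended rule for other missing values adds a choice that could be made after the data are seen.

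**Working it through.** **Inputs from the documents.** Response is HBV DNA below 10 IU/ml at week 24; the earlier outcome time point is week 12; baseline status is non-response in groups 2 and 3 and response in group 1; tests are generally two-sided at 0.05 (B.3). The documents give no loss rate, response rate or planned group size, so the plan has no figure on this point to reproduce. Its yearly count of 16,200 (0.30 × 54,000) is a screening estimate and does not bear on the matter.

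**Assumptions.** Baseline counts as a previous measurement, and week 12 is the first follow-up value. Except in step 5, loss is unrelated to outcome. All rates are illustrative. Loss is written as before week 12 + weeks 12 to 24.

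**Formula.** With d0 and d12 the shares lost in the two intervals, p12 and p24 the response rates, and b the baseline status (0 in groups 2 and 3, 1 in group 1):

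reported rate = (1 − d0 − d12) × p24 + d12 × p12 + d0 × b

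bias = d0 × (b − p24) + d12 × (p12 − p24)

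**Step 1: one group starting at or above the cut.**

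| p12 / p24 | Loss 5%+5% | Loss 10%+10% |
|---|---|---|
| 30% / 50% | 0.90×0.50 + 0.05×0.30 = 46.5% | 0.80×0.50 + 0.10×0.30 = 43.0% |
| 10% / 15% | 0.90×0.15 + 0.05×0.10 = 14.0% | 0.80×0.15 + 0.10×0.10 = 13.0% |
| 40% / 60% | 0.90×0.60 + 0.05×0.40 = 56.0% | 0.80×0.60 + 0.10×0.40 = 52.0% |

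**Step 2: group 1.** With b = 1 the first bias term is d0 × (1 − p24), which cannot be negative. Early loss pushes this group's rate up, not down.

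**Step 3: groups 2 and 3 compared, equal loss of 10%+10%.**
- True 60% v 15% (45 points): 52.0 − 13.0 = 39.0.
- True 60% v 50% (10 points): 52.0 − 43.0 = 9.0.

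**Step 4: unequal loss, 5%+5% in group 3 and 10%+10% in group 2.**
- No true difference, 30%/50% in both: 46.5 − 43.0 = 3.5 points.
- No true difference, 10%/15% in both: 14.0 − 13.0 = 1.0 point.
- Swapping the loss reverses both signs.
- True 10 points: 56.0 − 43.0 = 13.0; swapped, 52.0 − 46.5 = 5.5.
- True 45 points: 56.0 − 13.0 = 43.0; swapped, 52.0 − 14.0 = 38.0. At 43.0 the two groups' biases partly cancel.

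With an unpooled z test, the false 3.5 points reach two-sided P<0.05 in 11% of studies at 200 per group and 35% at 1,000. The false 1.0 point does so in 6% and 10%.

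**Step 5: loss related to outcome.** Suppose 20% are lost, retained patients respond at 60%, 36% of lost patients were responders when last seen, and 20% of them truly are at week 24. Reported: 0.80×0.60 + 0.20×0.36 = 55.2%. True: 0.80×0.60 + 0.20×0.20 = 52.0%. The rule now overstates.

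The rule can also be exactly right. At 30%/50% with loss split evenly it scores lost patients at (0.05×0 + 0.05×0.30) / 0.10 = 15%, so there is no bias if they truly respond at 15%, 35 points below the retained 50%. At 10%/15% the same sum gives 5%, 10 points below. The break-even depends on the scenario.

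**The case against.** The strongest reply is that the plan names no comparison. The main index is timed from a therapy adjustment, which refusers do not have, so the plainest reading is a single proportion among patients who change therapy. On that reading the non-informative examples for groups starting above the cut show understatement of 1 to 8 points (15.0 to 14.0 at the least, 60.0 to 52.0 at the most), and scoring early loss as failure is conservative. This largely stands. It limits the group 2 v group 3 results to a conditional statement. It does not remove the within-group bias, and step 5 shows that the rule is not conservative in every case.

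A reader might infer that the rule would manufacture a substantial difference between refusers and switchers. With loss of 2%+3% v 15%+10% and equal true response, the false gap would be 7.9 points at 30%/50% (48.4 − 40.5) and 10.5 at 50%/70% (68.0 − 57.5). The documents do not support this. It needs an inferred comparison, total loss of 5% against 25%, and patients who keep their regimen responding as often as those who change it. Nothing in the plan points to the last two.

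The choice of primary method is also partly a matter of preference. Counting missing as non-response is defensible for a single proportion. With unequal loss, however, it can exaggerate a gap: 0.90×0.50 − 0.80×0.50 = 5.0 false points, against 3.5 for carrying forward.

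**Conclusion.** The point holds: a single untested rule for lost patients, an unspecified rule for other missing values, and no sensitivity analysis on the main index. The rule biases the week-24 proportion whenever lost patients' last status differs from their week-24 status; where the two agree, there is no bias. In groups 2 and 3 the expected direction is downward if response is still rising and loss is unrelated to outcome. In group 1 a carried baseline value acts upward.

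For a group at 50% the understatement is 3.5 points with 10% lost and 7.0 with 20% lost; for a group at 15% it is 1.0 and 2.0. If groups 2 and 3 are compared, unequal loss is not needed for distortion: equal loss already shrinks a true difference. Unequal loss is needed only to create a gap where none exists. A modest difference could be altered materially, but one of 45 points would survive every example here. It would go too far to conclude that the study's result must be wrong, or that the error has a known sign. All sizes rest on assumed rates and on baseline counting as a previous measurement.

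**What to change.** - Replace both filling rules with one pre-specified primary method for week-24 response. One option is multiple imputation of the binary response, run by group, from week-12 response, baseline HBV DNA, entry NA and ALT. Include or pool centre only where cell sizes allow.
- Report loss by group and by interval (before week 12, weeks 12 to 24).
- Add a tipping-point analysis that varies the response of lost patients separately in each group and reports where the conclusion changes. Show missing counted as non-response as one bound.
- State whether the main index is a single-group proportion among patients who change therapy or a named between-group comparison. If it is a comparison, define a common time origin for patients who have no therapy adjustment.

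The cost is SAP wording and some extra analysis, with no new visits or data. Intervals will be slightly wider, and the primary analysis will rest on a missing-at-random assumption that cannot be tested, only stressed by the tipping-point analysis.
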